#### Withdrawal from the Optional Research Samples While Remaining in the Main Study

The subject may withdraw consent for optional research samples while remaining in the study. In such a case, the optional research samples will be destroyed. The sample destruction process will proceed as described above.

#### Withdrawal from the Use of Samples in Future Research

The subject may withdraw consent for use of samples for research (refer to Section 16.2.5, Long-Term Retention of Samples for Additional Future Research). In such a case, samples will be destroyed after they are no longer needed for the clinical study. Details of the sample retention for research are presented in the main ICF and in the separate ICF for optional research samples.

#### 11. STATISTICAL METHODS

Statistical analysis will be done by the sponsor or under the authority of the sponsor. A general description of the statistical methods to be used to analyze the efficacy and safety data is outlined below. Specific details will be provided in the Statistical Analysis Plan (SAP).

#### 11.1. Analysis Sets

The full analysis set (FAS) population includes all subjects who are randomly assigned to a treatment group, have received at least 1 dose of study drug and have a baseline HbA1c measurement.

The safety analysis set will include randomized subjects who take at least 1 dose of study drug.

The per protocol (PP) analysis set consists of all FAS subjects who complete the 26-week double-blind treatment phase and have no major protocol deviations that may affect the interpretation of the primary efficacy endpoint. Major protocol deviations will be defined in the SAP.

The primary efficacy analyses, to demonstrate the superiority of canagliflozin compared with placebo, will be based on the FAS population. Supportive analyses in the PP analysis set will also be performed for the primary endpoint of  $HbA_{1c}$ .

Efficacy data will be analyzed according to the initial randomization assignment, regardless of the actual treatment received. Safety data will be analyzed according to the predominant treatment received, in the event that subjects received a treatment other than that to which they were randomly assigned to receive. The approaches used to handle study deviations will be detailed in the SAP.

# 11.2. Sample Size Determination

The primary hypothesis of the study is that canagliflozin is superior to placebo in glycemic control, as measured by the change from baseline to Week 26 in HbA1c.

The sample size calculation is based on the 2-stage randomization design using a 2-sample, 2-sided t-test with Type 1 error rate of 0.05. Based on the following assumptions on treatment effect (0.4% to 0.5%) and an associated common standard deviation of 0.9% and assuming 50% of the subjects will meet the re-randomization criteria at Week 12, it is estimated that at least 66 subjects per group will be required to achieve approximately 85% power. To account for attrition due to study discontinuation in a longitudinal analysis (to be described below), a 10% sample size inflation factor is employed (Lu 2008), and a total of at least 146 subjects (73 per arm) will be randomized in this study.

Treatment group	Meeting re- randomization criteria at Week 12	Placebo-subtracted group difference in change in HbA 1c from baseline to Week 26
canagliflozin 100 mg to canagliflozin 100 mg	No	0.5%
canagliflozin 100 mg to canagliflozin 100 mg	Yes	0.4%
canagliflozin 100 mg to canagliflozin 300 mg	Yes	0.5%

For subjects who are on background metformin (with or without insulin), it is estimated that at least 33 subjects per group (after accounting for attrition due to study discontinuation) will be required to achieve approximately 85% power to assess the efficacy of canagliflozin on a background of metformin.

Treatment group (add-on to metformin)	Meeting re- randomization criteria at Week 12	Placebo-subtracted group difference in change in HbA 1c from baseline to Week 26
canagliflozin 100 mg to canagliflozin 100 mg	No	0.75%
canagliflozin 100 mg to canagliflozin 100 mg	Yes	0.65%
canagliflozin 100 mg to canagliflozin 300 mg	Yes	0.75%

The assumed treatment effect above is based on a subgroup analysis of subjects with baseline eGFR of  $\geq$ 90 mL/min/1.73m^2 from the add-on to metformin study of canagliflozin in adults (ie, Study DIA3006).

### 11.3. Efficacy Analyses

# 11.3.1. Primary Efficacy Endpoint

#### 11.3.1.1. **Definition**

The primary efficacy endpoint will be the change in HbA1c from baseline at Week 26.

#### **Estimand**

The primary efficacy estimand is described according to the following attributes:

• Population: children and adolescents ( $\geq 10$  to < 18 years) with T2DM who have an HbA1c  $\geq 6.5\%$  to  $\leq 11.0\%$ 

- Variable: change in HbA1c from baseline to Week 26
- Treatments: canagliflozin vs placebo
- Intercurrent event (events that preclude observation of the variable or affects its interpretation): treatment discontinuation or initiation of rescue medication, variable is used regardless of early treatment discontinues or initiation of rescue medication
- Treatment policy strategy: the measurements of the variable of interest are used regardless of the occurrence of the intercurrent event
- Population-level summary for the variable: the placebo-subtracted difference (ie, canagliflozin versus placebo) in least-squares mean change of HbA1c from baseline at Week 26 along with the 2-sided 95% CI

This estimand targets the effect of canagliflozin on the variable measured and follows an "ITT principle" strategy.

The main analysis of the primary efficacy outcome will be based on all HbA1c measurements (regardless of the occurrence of treatment discontinuation or initiation of rescue medication) and will employ pattern mixture modelling using multiple imputation methods. The imputed datasets will be analyzed using analysis of covariance (ANCOVA) with terms for treatment, stratification factors, and baseline HbA1c. Additional details will be specified in the SAP.

The following sensitivity analyses will also be performed using the primary estimand:

- The primary efficacy endpoint will be analyzed using a mixed model for repeated measures (MMRM) based on restricted maximum likelihood. The analysis will use the observed data and will include the fixed, categorical effects of treatment, stratification factors (ie, background AHA and age group), visit, and treatment-by-visit interaction, as well as the fixed, continuous covariates of baseline and baseline-by-visit interaction. An unstructured covariance will be used to model the within-patient errors. This sensitivity analysis will constitute the primary analysis based on a specific health authority request.
- The change from baseline in HbA1c will be analyzed using an ANCOVA model with treatment and the stratification factors as fixed effects and baseline HbA1c value as a covariate. The treatment differences in the least-squares means and the 2-sided 95% CI will be estimated based on this model. The last observation carried forward (LOCF) method will be applied when the Week 26 values are missing.

The following supplementary analysis will be performed using the primary estimand:

• A re-randomization test (Proschan 2011) (utilizing the MMRM as described above) will be used to determine the p-value for the primary efficacy comparison (ie, comparing all subjects who are randomized to canagliflozin to all subjects who are randomized to placebo). The re-randomization test will fix the observed HbA1c data, regenerate treatment assignments for the entire study using the same minimization algorithm employed in the study and compute the test statistics corresponding to the primary efficacy comparison. This process will be repeated at least 1,000 times. The p-value for the primary efficacy comparison will be defined as the proportion of re-randomized studies whose test statistic for that comparison is at least as extreme as that of the original treatment assignment.

[figure not shown]
The primary efficacy endpoint will also be performed in the subset of FAS subjects on a background of metformin (with or without insulin) using the main analysis methods described above. Analyses for the other AHA subgroups in the FAS may also be performed.

Additional details on the data handling rules (including the definition of data windows used for analysis) will be described in the SAP.

# 11.3.2. Multiplicity Adjustment

To strongly control the family-wise error rate at the 5% significance level, a sequential testing procedure as illustrated in Figure 2 below will be applied. The primary endpoint will be first tested in all subjects (ie, FAS), and if the results are significant (2-sided alpha level of 0.05), it will then proceed to test the subset of subjects on a background of metformin (with or without insulin).

Figure 2: Testing Sequence

The formal hypothesis testing above will be based on all randomized subjects in the FAS.

The comparisons by canagliflozin dose to placebo will also be presented and analyzed using the weights in the analyses described below.

- When comparing subjects who initially receive canagliflozin 100 mg with no dose increase to 300 mg to placebo: All subjects start with a weight of 1. After Week 12, subjects with an HbA1c ≥7.0% and eGFR ≥60 mL/min/1.73m² who are re-randomized to continue canagliflozin 100 mg will have a weight of 2. The subjects who are re-randomized to up-titrate to canagliflozin 300 mg will have a weight of 0.
- When comparing subjects who initially receive canagliflozin 100 mg followed by a dose increase to 300 mg to placebo: All subjects start with a weight of 1. After Week 12, subjects with an HbA1c ≥7.0% and eGFR ≥60 mL/min/1.73m² who are re-randomized to continue canagliflozin 100 mg will have a weight of 0 and those who are re-randomized to up-titrate to canagliflozin 300 mg will have a weight of 2.

As the secondary efficacy endpoints listed in Section 11.3.3, Secondary Efficacy Endpoints, are supportive in nature, no corresponding hypothesis testing will be performed, and therefore they are not included in the testing sequence above.

# 11.3.3. Secondary Efficacy Endpoints

The secondary efficacy endpoints at Week 26 and Week 52 include:

- Change from baseline in FPG
- The proportion of subjects with HbA1c <7.5%, <7.0%, and <6.5%
- Time to rescue and proportion of subjects receiving rescue therapy
- Percent change from baseline in body weight
- Change from baseline in BMI
- Percent change from baseline in lipids
- Change from baseline in systolic and diastolic blood pressure

The secondary efficacy endpoint at Week 12 and Week 52:

• Change from baseline in HbA1c

The estimands for the analysis of the secondary endpoints are the same as for the primary efficacy endpoint.

The categorical secondary efficacy endpoint of maintaining HbA1c <7.0% (and HbA1c <6.5% and HbA1c <7.5%) will be analyzed longitudinally using a generalized linear mixed model in the FAS population. The model will include the fixed, categorical effects of treatment, stratification factors (ie, background AHA and age group), visit, and treatment-by-visit interaction, as well as the fixed, continuous covariates of baseline and baseline-by-visit interaction. An unstructured covariance will be used to model the within-subject errors. The odds ratio and 2-sided 95% CI for the treatment comparisons at Week 26 (canagliflozin compared to placebo) will be estimated based on this model.

Continuous endpoints (except for triglycerides) will be analyzed with an MMRM model as described before in the FAS population. For the endpoints with post-baseline assessments taken only at Week 26 and Week 52, an analysis of covariance (ANCOVA) model similar to the primary efficacy endpoint will be used at Week 26. The least-squares means for the treatment comparisons and their 2-sided 95% confidence intervals will be estimated based on this model. The analysis of percent change in triglycerides may be based on nonparametric methods (given the anticipated skewed nature of this parameter) or alternative methods, to be further described in the SAP.

# 11.4. Pharmacokinetic Analyses

Concentrations will be reported for all subjects at all visits. Concentrations below the lower limit of quantification or missing will be labeled as such in the concentration database. Descriptive statistics, including arithmetic mean, SD, coefficient of variation, median, minimum, and maximum will be calculated and provided by treatment arm, and by treatment and background treatment. Population based PK modeling may be applied to the available plasma concentrations as needed.

# 11.5. Biomarker Analyses

Changes in serum osteocalcin and serum collagen type 1 CTx over time will be summarized by treatment group. Associations between baseline levels and changes from baseline in select markers and clinical response at 26 and 52 weeks of treatment will be explored. Biomarker analyses will be summarized in separate technical reports.

Biomarker results will be presented in a separate report.

#### 11.6. Safety Analyses

Subjects in the safety analysis set (defined as subjects who are randomized and take at least 1 dose of study drug) will be included in the denominators for the summaries of adverse event, exposure, and concomitant medication data. There will be no imputation of missing values for clinical safety laboratory test results and vital sign measurements, in the safety analyses. Descriptive statistics for clinical laboratory test results and vital sign measurements will be presented based on measurements on study drug, including up to a maximum of 2 days after the last dose of study drug, as well as all measurements regardless of the time of the last dose of double-blind study drug. All safety analyses (except hypoglycemia) will be summarized regardless of the use of rescue medication; given the potential confounding due to rescue medication, analyses related to hypoglycemia will only be presented prior to rescue medication.

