## **Hypoglycemic Episodes**

Hypoglycemic episodes are collected on a separate eCRF and are also collected on the adverse event eCRF (for all such events considered as adverse events by the investigator). The primary analysis of hypoglycemia will be based upon data from the hypoglycemia eCRF (and not from the adverse event database). No reconciliation of hypoglycemia data from the adverse event eCRF and the hypoglycemic eCRF will be performed (except to assure that all adverse events of hypoglycemia are also recorded on the hypoglycemia eCRF).

Hypoglycemic episodes will be classified as *either* biochemically documented (ie, a hypoglycemia episode with a concurrent reported glucose value of ≤70 mg/dL [≤3.9 mmol/L]) and/or severe. The primary hypoglycemic analysis of interest will be all biochemically documented hypoglycemic episodes regardless of the presence of symptoms plus all severe hypoglycemic episodes. For each type of hypoglycemia, the percentage of subjects with at least one event will be summarized by treatment group. The hypoglycemic episode rate per subject year exposure, based on the number of episodes adjusted by exposure duration, will be reported by treatment group for each classification of hypoglycemia. (See Attachment 4, Hypoglycemia: Definitions, Symptoms, and Treatment).

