6.1. Adverse Events

Adverse events will be summarized for the 26-week core double-blind treatment period and for the 52-week double-blind treatment phase separately. AEs will be coded using the latest version of the Medical Dictionary for Regulatory Activities (MedDRA) at the time of database lock. Therefore, the preferred terms presented in Attachment 2 may be updated to reflect such updates. A treatment-emergent AE (TEAE) is defined as an adverse event with an onset after the initiation of double-blind study medication and before the last study medication date + 30 days. AEs with a start date prior to initiation of double-blind study medication which are subsequently reported to have either an increase in intensity or change in attribution in relationship to study medication (ie, no attribution to possible, probably, very likely) after the initiation of double-blind study medication will also be considered as TEAEs. Treatment-emergent AEs before the initiation of rescue therapy and TEAEs regardless of rescue therapy will be summarized separately for the 26-week core double-blind treatment period and for the 52-week double-blind treatment phase.

The overall incidence (ie, number and percent of subjects with one or more AE in each category) of AEs, AEs leading to discontinuation of study medication, drug-related AEs, drug-related AEs leading to discontinuation of study medication, serious AEs, serious AEs leading to discontinuation of study medication, serious drug-related AEs, serious drug-related AEs leading to discontinuation of study medication, serious drug-related AEs, serious drug-related AEs leading to discontinuation of study medication, serious drug-related AEs, serious drug-related AEs leading to discontinuation of study medication and deaths, will be summarized by treatment group.

AEs by SOC (ie, number and proportion of subjects with one or more AEs within a SOC) will be summarized by treatment group.

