6.1.2. Hypoglycemia

Hypoglycemia episodes are collected by a specific, dedicated eCRF. Investigators are also asked to report episodes of hypoglycemia as an adverse event if they evaluate the episode as such. Analyses discussed below are based upon events reported through the hypoglycemia eCRF. Note that reconciliation will be performed to assure that all events reported as AEs are also recorded on the hypoglycemia eCRF.

A subject will be counted as having a documented hypoglycemia episode when there is either a biochemically confirmed hypoglycemic episode (ie, concurrent fingerstick glucose or plasma glucose \leq 70 mg/dL [3.9 mmol/L]), and/or a severe hypoglycemic episode, as reported on the hypoglycemia eCRF, as follows:

- Biochemically documented hypoglycemia episode: a hypoglycemia episode with a concurrent reported glucose value of \leq 70 mg/dL (3.9 mmol/L), regardless of whether the episode is associated with symptoms (symptomatic hypoglycemia) or not (asymptomatic hypoglycemia)
- Severe hypoglycemia episode: a hypoglycemia episode that has
 - the answer "Yes" for "Convulsions/Seizure" or "Loss of consciousness/Coma" to the question "Any signs/symptoms present?", or
 - check "Subject was not Capable of Treating Self and Required Assistance" to the question "If treatment given indicate assistance needed."

Only treatment-emergent hypoglycemia episodes, reported on the eCRF for hypoglycemia, will be summarized. Treatment-emergent is defined the same way as treatment-emergent AEs (defined in Section 6.1). Given the potential confounding of rescue medication to the treatment effect, treatment-emergent hypoglycemia episodes before the initiation of rescue therapy will also be summarized.

Because the background AHA may affect the risk of hypoglycemia, treatment-emergent hypoglycemia episodes will be summarized for both 26-week core double-blind treatment period and 52-week double-blind treatment phase by the following background AHA groups at randomization before the initiation of rescue therapy and regardless of rescue therapy.

- Diet and exercise only; or metformin monotherapy.
- On insulin (with or without metformin).

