The percentage of subjects with documented hypoglycemia episodes (ie, biochemically documented and/or severe) and subjects with biochemically documented, and with severe hypoglycemia episodes separately, will be summarized by treatment group. For subjects with biochemically documented hypoglycemia episodes, the percentage of subjects will be summarized for each of the following glucose levels (\leq 70 mg/dL [3.9 mmol/L], <56 mg/dL [3.1 mmol/L], and <36 mg/dL [2.0 mmol/L], "Low" results will be included in all three categories) by treatment group. For subjects with severe hypoglycemia episodes, the percentage of subjects by each answer of the 2 questions for severe hypoglycemia on the eCRF will be summarized by treatment group. Event rate by person-year (total number of episodes/total exposure) will be calculated by treatment group separately for documented and for severe hypoglycemia.

Subjects who had 0, 1, 2, or \geq 3 documented episodes and subjects who had 0, 1, 2, or \geq 3 severe hypoglycemic episodes will be summarized by treatment group.

In addition, the incidence of all episodes of hypoglycemia reported on the eCRF for hypoglycemia will be summarized (this includes events without concurrent fingerstick glucose reported and events with fingerstick glucose >70 mg/dL [3.9 mmol/L]) by treatment group.

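### The pre-rescue hypoglycemia and adverse-event percentages take no account of time at risk, which will be shorter on placebo if placebo is rescued more; and the Protocol and SAP disagree on whether hypoglycemia is shown only before rescue

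*Protocol*

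**What the plan says.** **Protocol.** Section 11.6 sets one rule for hypoglycemia and the opposite rule for everything else: "All safety analyses (except hypoglycemia) will be summarized regardless of the use of rescue medication", whereas "analyses related to hypoglycemia will only be presented prior to rescue medication". The reason given is confounding by rescue medication. The Synopsis repeats the rule. The paragraph on hypoglycemic episodes then specifies two measures. The first is a crude percentage: "For each type of hypoglycemia, the percentage of subjects with at least one event will be summarized by treatment group". The second is a rate: "The hypoglycemic episode rate per subject year exposure, based on the number of episodes adjusted by exposure duration, will be reported by treatment group". It does not say where exposure ends for a rescued subject.

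**SAP.** Section 6.1.2 summarizes all treatment-emergent hypoglycemia and adds that "treatment-emergent hypoglycemia episodes before the initiation of rescue therapy will also be summarized". Its tables by background therapy are given both before and regardless of rescue, for 26 and for 52 weeks. It also plans a rate per person-year, as total episodes over total exposure. Section 6.1 does the same for adverse events: "Treatment-emergent AEs before the initiation of rescue therapy and TEAEs regardless of rescue therapy will be summarized separately". It then screens adverse events with 95% confidence intervals for the arm difference, without saying which of the two sets is screened. Section 4.4 defines treatment duration from first to last dose.

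**Rescue.** Under Protocol 6.2.2 (Table 2), a subject qualifies on an HbA1c rise from baseline above 0.8% (baseline below 9.0%) or above 0.5% (baseline 9.0% or more). Double-blind drug continues after rescue.

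**The concern.** A percentage with at least one event grows with the time each subject is watched. The pre-rescue tables end that time at rescue but keep the whole safety set as denominator. Rescue is a consequence of poor glycemic response, so the cut is not neutral between arms. If placebo reaches it sooner, placebo subjects have less time to record a first event, and an excess can appear on canagliflozin where none exists.

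Two things raise the stakes. Safety and tolerability is a primary objective, and the discarded time is still time on study drug. Rescue may also involve a change in insulin, and Protocol 16.1 says that canagliflozin given with insulin may increase hypoglycemia risk. The Protocol rule, applied alone, would leave that period out of every hypoglycemia table.

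**Working it through.** **1. The plan's own figure.** The documents give no expected rescue or hypoglycemia rate. The only figure to reproduce is the efficacy sample size (Protocol 11.2), which supplies the effect and SD used below. Mean effect = 0.5×0.5 + 0.5×(0.5×0.4 + 0.5×0.5) = 0.475. With SD 0.9, two-sided alpha 0.05 and 66 per group, the noncentral t gives power 0.853, which agrees with the stated 85%.

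**2. Does rescue depend on treatment?** Assume zero mean change on placebo and the plan's SD at a single visit. P(change > c) = 1 − Φ((c − μ)/0.9).

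| Threshold | Placebo (μ = 0) | Canagliflozin (μ = −0.475) |
|---|---|---|
| >0.8% | 1 − Φ(0.889) = 18.7% | 1 − Φ(1.417) = 7.8% |
| >0.5% | 1 − Φ(0.556) = 28.9% | 1 − Φ(1.083) = 13.9% |

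On the plan's own effect size, placebo qualifies about twice as often.

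**3. Closed-form illustration.** Give both arms the same event hazard h, and let rescue occur at hazard r over T weeks. Then
- crude pre-rescue percentage = h/(h+r) × (1 − exp(−(h+r)T));
- mean pre-rescue follow-up = (1 − exp(−rT))/r.

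Take T = 52, a true risk of 20% in both arms (h = −ln 0.8/52 = 0.00429), and assumed rescue of 10% on canagliflozin (r = 0.00203) and 30% on placebo (r = 0.00686).
- Canagliflozin: 0.679 × 0.280 = 19.0%, mean follow-up 49.4 weeks.
- Placebo: 0.385 × 0.440 = 16.9%, mean follow-up 43.7 weeks.
- False excess on canagliflozin: 2.1 points.

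With assumed rescue of 5%/15%, 10%/30% or 10%/45% (canagliflozin/placebo) and true risks of 10% to 40%, the excess is 0.5 to 7.3 points. With equal rescue (20%/20%) it is zero.

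**4. Simulation from the plan's thresholds.** 200,000 subjects per arm, HbA1c change at Weeks 6, 12, 20, 26, 34, 42 and 52, SD 0.9, and the effect rising linearly to 0.475 at Week 12. Assumed: within-subject correlation 0.6 to 0.9, 20% to 40% of subjects with baseline 9.0% or more, and 50% or 100% of qualifying subjects rescued.
- Rescued by Week 52: placebo 17–54%, canagliflozin 9–33%.
- Share of follow-up falling after rescue: 13–37% against 7–23%.
- False excess at Week 52: about 1.5 to 4 points for a 30% event, and 2.9 to 7.7 points for a 60% event.
- False excess at Week 26, same hazards: 0.6 to 1.5 and 1.3 to 3.1 points. The 30% event then has a 26-week risk of 1 − √0.7 = 16.3%.

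**5. What if rescue-prone subjects differ?** Let 30% of each arm be rescue-prone, with all of them rescued at mid-period on placebo and one third of them (10% of the arm) on canagliflozin, and a 30% risk in the other subjects. At equal hazard the excess is 2.7 points. If the rescue-prone have 0 to 0.5 of the others' hazard, it is 0 to 1.6 points.

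**6. Does the person-year rate cure it?** Expected pre-rescue episodes are the hazard times mean pre-rescue follow-up. Divided by pre-rescue time, the rate ratio is 1.00. Divided by full treatment duration, as SAP 4.4 would define it, the ratio equals the ratio of follow-up times: 49.4/43.7 = 1.13 in the example, and 1.06 to 1.26 over the assumed rescue rates. The bias then returns.

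**7. Is the regardless-of-rescue view free of bias?** With 20% risk and rescue of 10% and 30%, suppose the hazard doubles or triples after rescue. The percentages become 20.8% v 22.6%, or 21.6% v 24.9%. Canagliflozin then looks better by 1.8 to 3.3 points.

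**The case against.** **The SAP already covers this.** Protocol section 11 describes itself as general and leaves detail to the SAP, which is later (2023 against 2020) and plans hypoglycemia regardless of rescue. This largely stands: an equal-window hypoglycemia comparison will exist. It does not remove the conflict with the Protocol's wording, and it leaves the pre-rescue percentages unadjusted.

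**The Protocol has an exposure-adjusted rate.** A reader might infer that it permits no other hypoglycemia comparison than the crude percentage. That is wrong. But the same rule confines the rate to the pre-rescue period, and neither document ends its denominator there.

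**Adverse events are not affected overall.** This stands. The Protocol's rule for adverse events is regardless of rescue, and pre-rescue tables appear only in the SAP, beside the others. No safety hypothesis is tested, and the SAP describes the confidence intervals as a filter. What remains is that the filter's table set is unnamed.

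**Direction and size are assumed.** Rescue by arm is an endpoint with no stated rate, and rescue is partly at the investigator's discretion. The direction is therefore conditional, though on the effect the trial is powered to show. The size is modest: 1.5 to 4 points is about 1 to 3 subjects of 73, against a 95% half-width near 1.96 × √(2×0.3×0.7/73) = 15 points. Small size is a reason for proportion, not for leaving a known directional error in place.

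**The pre-rescue rule has a reason.** It avoids confounding by rescue, and step 7 shows that this confounding could hide harm. This stands, and argues for showing both views.

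**Conclusion.** The point holds in a limited form. The pre-rescue percentages for hypoglycemia, and the SAP's for adverse events, are not comparable between arms if rescue differs by arm. If placebo is rescued more, they are biased against canagliflozin, by the amounts in step 4 for the assumed rescue patterns, and by less or nothing if rescue-prone subjects are at low risk. Those figures rest on the plan's SD and effect, zero placebo drift, and assumed correlation, baseline mix and uptake of rescue. The conflict between the Protocol's exclusive pre-rescue rule and the SAP's two presentations rests on no assumption.

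Three stronger readings are not supported. The trial does not lack an equal-window hypoglycemia comparison, because the SAP plans one. The adverse-event comparison as a whole is not biased by rescue. And the regardless-of-rescue view cannot be ranked as the unbiased one, since rescue insulin can tilt it towards canagliflozin. The correction is worth making because it is cheap, not because the error is large.

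**What to change.** 1. **SAP 6.1 and 6.1.2.** Beside each pre-rescue percentage, give a Kaplan-Meier incidence at Weeks 26 and 52, or first events per person-year. Censor at the earliest of rescue start, last dose plus 30 days, or end of the period. Report the arm difference with its 95% confidence interval. Where a person-year rate is given for the pre-rescue period, end its denominator at rescue.
2. **Protocol 11.6 and Synopsis.** Reword the sentence so that hypoglycemia is presented both regardless of rescue and prior to rescue, matching the SAP.
3. **SAP 6.1.** State that the confidence-interval screen for adverse events uses the regardless-of-rescue tables, consistent with the Protocol's rule for adverse events.
4. **Interpretation.** Show both hypoglycemia views and state the limit of each: rescue insulin can affect the one, and censoring at rescue assumes that rescue is unrelated to event risk in the other.

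**Cost.** One Protocol sentence in two places, some SAP wording and a few table columns. Rescue initiation is already recorded on the eCRF (Protocol 6.2.2), and Kaplan-Meier methods are already planned for time to rescue (SAP 5.3.2). No new data are needed; the tables become slightly longer.
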